2.2.2 Dosing Rationale

Dosing will be in the range approved by the FDA. For Vivitrol only one dose strength of 380 mg of naltrexone is available. For Brixadi, a combination of weekly (8mg, 16mg, and 24mg) and monthly doses of 64mg, 96mg, or 128mg will be used in the range and manner approved in accordance with the FDA and EMA]

2.2.3 Clinical Adverse Event Profile

Vivitrol® (XRNTX) is naltrexone for extended-release injectable suspension. Vivitrol is approved by the FDA for the treatment of opioid use disorder. It is manufactured and marketed in the US by Alkermes plc. Full prescribing information is available at <https://www.vivitrol.com/>

Brixadi® (CAM 2038, XRBUP), is prolonged-release buprenorphine solution for injection. On May 23, 2023, the U.S. FDA granted approval of Brixadi to Braeburn Inc for the treatment of Opioid Use Disorder . . Information on safety and adverse events profile for Brixadi is available at <https://braeburnrx.com/braeburns-brixadi-buprenorphine-extended-release-subcutaneous-injection-ciii-receives-fda-approval-for-moderate-to-severe-opioid-use-disorder/>

2.2.4 Dosing Rationale

Dosing will be in the range approved by the FDA. For Vivitrol only one dose strength of 380 mg of naltrexone is available. For Brixadi, a combination of weekly doses (8mg, 16mg, and 24mg) and monthly doses of 64mg, 96mg, or 128mg mg will be used in the range and manner approved in accordance with the FDA and EMA]

2.3 Risk/Benefit Assessment

2.3.1 Known Potential Risks

Medications (please see Sections 2.2.1 and 2.2.2):

Participants who are opioid-positive upon screening will undergo office-based treatment using FDA-approved generic medications to alleviate opioid withdrawal symptoms as determined by the study physicians, following symptom-triggered approach that includes clonidine 0.1 mg tid, dicyclomine 20 mg qid, clonazepam 0.5 mg q12 hrs PRN, diphenhydramine PRN, non-steroidal

anti-inflammatory drugs (NSAID's) PRN, trazodone 50 mg qhs and oral hydration solutions. Common side effects of these medications include over sedation and hypotension. These will be prevented by proper patient education and communication, and frequent medical monitoring.

Investigational Agent:

XRBUP (Brixadi) is an extended-release formulation of buprenorphine. It is known as CAM 2038 and brand name Buvidal (EU) and Brixadi (US). CAM 2038 has been approved as Buvidal for opioid use disorder by the European Medicines Agency (MEA) and on May 23, 2023, The U.S. Food and Drug Administration granted approval of Brixadi to Braeburn Inc. It is administered by subcutaneous (SC) injection. It is available in multiple concentration and duration of action. For the present proposal we will use either the 64mg, 96mg, or the 128mg monthly dose. Braeburn, the US manufacturer of CAM 2038, has agreed to provide the study medication at no cost (See letter of support).

The most important and nevertheless rare side effects of buprenorphine are (1) precipitated opioid withdrawal; (2) anxiety; (3) pain and infection at the injection side, (4) liver toxicity in cases of compromised liver function. These will be minimized by the following steps:

Although complete lack of physiological dependence is not required for buprenorphine induction in the clinic, in order to avoid selection bias between XRNTX and XRBUP, all participants will undergo complete detoxification from opioids. This will be confirmed by an opioid-negative urine test or self-report of no opioid use in the last 5-7 days. Naloxone challenge test would not be necessary for CAM 2038 induction.

Anxiety is usually self-limited and will be treated symptomatically, initially with the weekly psychotherapy and if necessary, with medications indicated for this purpose.

Daytime sedation is uncommon and usually temporary. If it persists, patient will be interviewed again about concomitant sedative medications or alcohol. If these or other unrelated causes such as insomnia are not identified, the PI will determine whether it is necessary to exclude the participants from the study.

Meticulous injection technique: our experienced personnel who has administered thousands of Vivitrol injections without ANY complications over a decade, psychoeducation

Applying the exclusion criterion regarding elevated liver function tests labs described in the Exclusion Criteria section above.

Opioid overdose is a feared complication of OUD in general. In the context of the present study, overdose needs to be considered in two settings: during treatment and after participation ended. Individuals receiving buprenorphine or naltrexone are unlikely to experience opioid overdose during treatment, because buprenorphine is a partial agonist whose antagonist properties increase in a dose-dependent fashion and naltrexone is an antagonist that blocks the effects of illicit opioids. Buprenorphine treatment discontinuation does not lead to precipitous increase in sensitivity to illicit opioids. Individuals formerly treated with XRNTX do lose their tolerance to opioids and are therefore at an increased risk of opioid overdose if they discontinue MAT

treatment abruptly and usually against medical advice. Nevertheless, studies found that the rate of opioid overdoses after XRNTX discontinuation is actually lower than in the control groups. However, to minimize the risk of overdose, participants completing the study will be referred to the clinical program of their choice using a “warm-handoff” procedure that will include (1) beginning to make arrangements for post-study referral before the effects of XRNTX or XRBUP wear off allowing one month for the project coordinator and the participant to establish clinical treatment (2) monitoring and assisting participants in making their follow up appointment and escorting them to their first appointment as needed (3) Providing psycho-education about opioid overdose risk and provide prescriptions for the nasal Naloxone spray used as a rescue in case of an overdose.

XRNTX (Vivitrol) is an FDA-approved medication for opioid relapse prevention (<https://www.vivitrol.com/content/pdfs/prescribing-information.pdf>.) It is a suspension of 380 mg of naltrexone in a nanoparticle slow release vehicle, for intramuscular injection. The most important and nevertheless rare side effects are (1) precipitated opioid withdrawal; (2) anxiety; (3) pain and infection at the injection side, (4) liver toxicity in cases of compromised liver function and (5) loss of opioid tolerance and therefore greater risk of opioid overdose after study completion or in case of drop out. These will be minimized by the following measures:

Ensuring that the participant is not physiologically opioid dependent, by obtaining an opioid-negative urine test, self-report of no opioid use in the last 5 days (7 days for buprenorphine and methadone) and a negative naloxone challenge test (Langleben et al *Addiction Biology* 2014).

Anxiety is usually self-limited and will be treated symptomatically, initially with the weekly psychotherapy and if necessary, with medications indicated for this purpose.

Meticulous injection technique: our experienced personnel who has administered thousands of Vivitrol injections without ANY complications over a decade, psychoeducation

Applying the exclusion criterion regarding elevated liver function tests labs described in the Exclusion Criteria section above.

Risks of the study unrelated to the investigational product:

- 1) Exposure to high magnetic fields: The Siemens Magnetom Prisma 3 Tesla MRI scanner we will use in the study is a clinical MRI system approved by the FDA. Information about this scanner is available on manufacturers website: <https://www.siemens-healthineers.com/en-us/magnetic-resonance-imaging/3t-mri-scanner/magnetom-prisma>
- 2) FDA guidelines and the IRB committees consider this scanner to be a minimal risk device. Specific Absorption Rates (SAR) of electromagnetic energy by the body is controlled by a directional coupler that serves as a circuit breaker that switches the magnet off, if the local SAR exceeds the FDA limit of 8 watt/kg in any gram of tissue. The exposure characteristics are kept on file with a copy of the consent form at the University of Pennsylvania Center for MRI and Spectroscopy (CAMRIS). Although pregnancy is not a contraindication for MRI, pregnant women will not be eligible for XRNTX and therefore, screened out prior to them being considered for our study.

- 3) Participants who successfully complete detoxification, will undergo a neuroimaging session immediately followed by induction to XRNTX or XRBUP over a period of up to 14 days, which will include oral Naltrexone 50 mg for the XRNTX group followed by the 1st injection of XRNTX, or by injection of one or more weekly XRBUP in 8mg, 16mg or 24 mg strength with the total weekly dose not to exceed 32mg, followed by an injection of monthly XRBUP in 64, mg, 96mg, or 128mg strength (**Figure 1**). If deemed clinically necessary, induction to XRBUP may be extended by up to one week, using the same weekly Bixadi schedule. Buprenorphine/naloxone (Suboxone) is an FDA-approved sublingual form of buprenorphine that may be used during the induction if clinically indicated. Total duration of induction onto XRBUP will not exceed 14 days. Participants who are unable to complete the detoxification or induction will be excluded from the study and referred to a clinical addiction program for continuation of treatment as indicated. Suspected adverse reactions to any of the medications used in the study will be reported appropriately to the IRB, FDA at [name] or www.fda.gov/medwatch, Alkermes, plc at [name] or email: [contact] or both or Braeburn Inc at [name] .
- 4) Emotional discomfort and drug craving: Viewing drug-related images (cues) can sometimes trigger drug-related craving in participants with a drug-use history. This craving may cause some emotional and physiological arousal, but it does not pose a medical risk. Our standard practice is to have a trained clinician available in the event that the participant is still experiencing continued arousal or discomfort, either from the images or for any other reason, at the end of the imaging session. If the participant is still aroused, the clinician has a number of psychological strategies (deep relaxation, imagery, distraction, consequences tools, etc.) that can quickly help the subject inhibit craving and feel more comfortable and in control of her/his feelings. Taking these precautions increases the participant's level of comfort and safety. After testing hundreds of participants over more than a decade, none has ever dropped out as a consequence of drug-related images exposure session. We have demonstrated sessions handled with these precautions do not lead to an increase in drug use. There is a small chance that participants may become upset when discussing their history of drug use or other behaviors. We will discontinue administration of research instruments if a subject shows discomfort. If necessary, the investigators who are clinicians with expertise in addictions, will work with the participant to alleviate any concerns.
- 5) Confidentiality: There is a potential risk of a loss of confidentiality in any research participation. As our subjects carry a substance abuse diagnosis, this is a risk we take especially seriously. Following completion of an imaging session, raw data will immediately be transferred to electronic storage by the MR technician for later processing. This storage is in a locked room with access limited to the investigators and data processors. Subjective and physiological data are likewise kept in a locked area accessible only to the investigators/data processors. No published or presented materials will identify subjects by names, initials, or any other means that could be used to identify the participant. As part of consent procedures, patients will be advised of precautions taken to preserve confidentiality. Further, all participants in the data collection procedures have been instructed to not divulge any information concerning subjects to any person or agency without the written and explicit consent of the subject.

These procedures have been effective in completely protecting patient information in past studies. All study staff receive Good Clinical Practice and Human Subjects Protection training as well as HIPAA privacy training before working with any subjects. All medical records and research information will be kept confidential.

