4 STUDY PLAN

4.1 Study Design:

Single-blind, prospective study with Phase 1 (N = 60) to show feasibility and Phase 2 (N = 200) to confirm Phase 1 findings if they meet the milestones of effect size. This is to comply with the structure of the two-phase R61/R33 NIH funding mechanism. Both Phases will use the same sequence of data collection ([Section 3.1, Figure 2](#)).

Rationale for the study duration: Early medication effects are considered to be strong predictors of long term effectiveness both at the clinical (e.g. tolerability and symptom relief) and at the neural systems and pharmacodynamic levels (McDermott et al 2015). XRNTX exhibits high drop-out rate in the first 2 months of treatment, with 50% to 75% retention at the 3rd XRNTX injection (Wang et al 2015, Lee et al 2017). In a trial of sublingual buprenorphine, retention at 3 months was approximately 75% and relapse rates defined as repeated opioid positive urines were almost unchanged between 3 and 6 months time points (Lee et al 2017). Thus, a 70-day follow up period provided by two monthly XRNTX or XRBUP injections is a necessary and sufficient time window for a neurobiological evaluation of the mechanisms of relapse vulnerability while minimizing the effect of unrelated variables such as change in family, employment or medical status, on the outcome variable. We optimize the two-phase design by designing experiments that would generate data that could serve two purposes: the initial Phase 1 exploratory and milestone target and then part of the Phase 2 sample that would address confirmatory questions that require a sample size that neither phase could reach separately.

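### Abstinence is confirmed more strictly for XRNTX than for XRBUP, and as written the extra checks can remove XRNTX participants after randomisation and from the only analysis set

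*Combined protocol and SAP*

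**What the plan says.** Section 2.3.1 gives the purpose of the common run-in: "in order to avoid selection bias between XRNTX and XRBUP, all participants will undergo complete detoxification from opioids". It then sets the standard of proof: "This will be confirmed by an opioid-negative urine test or self-report of no opioid use in the last 5-7 days". For the buprenorphine arm it adds: "Naloxone challenge test would not be necessary for CAM 2038 induction".

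Under the XRNTX heading of the same section, freedom from physiological dependence rests on three checks together. The first two are "obtaining an opioid-negative urine test, self-report of no opioid use in the last 5 days", with the window lengthened to a week where the opioid was methadone or buprenorphine. The third is joined to them in these words: "and a negative naloxone challenge test".

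Section 6.1 (withdrawal management and induction) detoxifies all participants and randomises after abstinence from illicit opioids. It does not name the challenge as a condition. The Schedule of Activities (13.1) puts screening, detoxification and randomisation in one column and has no row for the challenge.

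Three rules govern early losses:
- Section 2.3.1: "Participants who are unable to complete the detoxification or induction will be excluded from the study".
- Section 7.2: people randomised but not injected may be replaced. The reason for withdrawal goes on the CRF.
- Section 9.3: the only analysis population is randomised participants who received study drug at least once. Study drug is not defined.

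**The concern.** The run-in is meant to bring both arms to the same starting point, but it is verified to a looser standard than one arm needs. Under the rules as written, someone who qualifies on self-report with a positive urine can stay if allocated to XRBUP and must be stopped if allocated to XRNTX. The challenge is required for one drug and waived for the other, so it can be applied by arm only once allocation is known, unless everyone is tested first. No section says that.

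XRNTX participants removed this way would probably be those less securely abstinent. If they are also likelier to relapse, the remaining XRNTX arm looks better than the randomised one. Nothing requires these losses or replacements to be reported by arm, so a reader of the results could not see how large the step was.

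**Working it through.** **1. The rules side by side**

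| Step | XRBUP | XRNTX |
|---|---|---|
| Urine and self-report (2.3.1) | either one | both |
| Naloxone challenge (2.3.1) | waived | must be negative |
| Timing relative to randomisation (6.1, 13.1) | abstinence comes before it | extra checks not dated |
| First induction product (2.3.1, 6.1) | weekly XRBUP injection | oral naltrexone for 7-10 days, then injection |
| Randomised, no injection (7.2) | may be replaced | may be replaced |
| Analysis set (9.3) | needs a dose of study drug | needs a dose of study drug |

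The loss rules are common to both arms, but the checks that feed them are not. The induction products add a second asymmetry. Section 2.3.1 describes induction as a period "which will include oral Naltrexone 50 mg for the XRNTX group followed by the 1st injection of XRNTX". If oral naltrexone does not count as study drug, XRNTX induction failures in that window leave the analysis set, whereas an XRBUP participant who has had a weekly injection is already in it.

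**2. Group by Session contrast (section 9.1)**

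A difference between arms at PRE does not by itself bias a comparison of changes. Let f be the share of randomised XRNTX participants removed, and D the difference in mean change between those kept and those removed, in SD units. The XRNTX mean change then shifts by f × D. Neither value is in the documents; both are assumed here.

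| f | D | Shift (SD) | Share of planned d = 0.42 (9.2) |
|---|---|---|---|
| 5% | 0.2 | 0.010 | 2.4% |
| 5% | 0.5 | 0.025 | 6.0% |
| 10% | 0.2 | 0.020 | 4.8% |
| 10% | 0.5 | 0.050 | 11.9% |

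With 80 per arm, 5-10% is 4-8 people. The standard error of d is about √(2/80) = 0.16, so the largest shift shown is 0.05/0.16, about a third of one standard error. If D = 0 there is no shift.

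**3. Group term for treatment failure (section 9.1)**

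Assume the same true failure rate p in both arms, and take the extreme in which everyone removed would have failed. Among those kept, the XRNTX odds of failure are (p − f)/(1 − p). The XRBUP odds are p/(1 − p). The ratio is (p − f)/p = 1 − f/p. Replacing those removed restores the number but not the composition, so the ratio is unchanged.

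For p, section 4.1 reports the XRNTX drop-out pattern in earlier studies, "with 50% to 75% retention at the 3rd XRNTX injection". That implies dropout of 25-50%. The outcome in section 9.1 also counts refusal, two or more positive urines and repeated self-reported use, so p is at least the dropout rate.

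| p | f = 5% | f = 10% |
|---|---|---|
| 0.50 | 1 − 0.05/0.50 = 0.90 | 1 − 0.10/0.50 = 0.80 |
| 0.75 | 1 − 0.05/0.75 = 0.93 | 1 − 0.10/0.75 = 0.87 |

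If those removed would have failed at rate p like everyone else, the ratio is 1.00. For scale, the power statement in section 9.1 assumes a Group odds ratio of 1.25, whose reciprocal is 0.80.

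**The case against.** The timing is inferred. Section 2.3.1 is risk-mitigation text. The operative procedure in 6.1 randomises only after abstinence, and 13.1 schedules urine and timeline follow-back for everyone at screening and again at day 0. The site may already require both from all participants before allocation. That stands: in that case only the challenge is arm-specific, and it would be given to people already judged abstinent.

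The challenge is a safety test that naltrexone needs and buprenorphine does not. That also stands, and it is a reason to keep it. XRBUP participants can be lost at induction too, but not through these checks, so the losses need not balance.

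The Group main effect on failure is not a named hypothesis. H2a concerns the neural variables and their interaction with Group. The change scores also need the second scan at day 55, so later dropout (25% anticipated in section 9.1) may be a larger selection step. Both points are fair and limit the consequence.

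Section 9.4.1 plans selection models, weighting and a complier analysis. These address discontinuation and non-adherence, and none is stated to bring back people who never entered the section 9.3 population. Counting refusal and dropout as failure helps only for people in that population.

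A reader might infer that the fMRI contrast is materially biased, or that the failure odds ratio could fall to 0.60 (f = 10%, p = 25%). The documents support neither. No value of f or D is given, and p = 25% is a dropout-only rate used for a composite that must fail at least as often.

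**Conclusion.** The point holds as a gap in the rules. As written, XRNTX participants alone can be filtered after allocation, replaced and dropped from the only analysis set. It is certain that the two standards differ and that the XRNTX checks are undated. It is not established that the urine and self-report part acts after randomisation, or how many people would be removed.

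The size cannot be derived from the documents. The effect on Group by Session is probably small, and zero if those removed would have changed no differently. The Group term for treatment failure is biased in favour of XRNTX if those removed were likelier to fail. With f of 5-10% the worst case is about 0.90-0.80 at p = 0.50 and 0.93-0.87 at p = 0.75. These figures assume no true arm difference and that everyone removed would have failed. The correction should be made because the plan names this bias as one to avoid and the change is cheap.

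**What to change.** - **Sections 2.3.1 and 6.1:** before randomisation, require from every participant both an opioid-negative urine and self-report of no use for 5 days (7 for buprenorphine and methadone).
- **Sections 6.1 and 13.1:** keep the naloxone challenge as an XRNTX safety check and date it before the first oral naltrexone dose.
- **Section 9.3:** define study drug as the first induction dose in either arm, oral naltrexone or weekly XRBUP.
- **Section 7.2:** report randomised participants who do not start, and any replacements, by arm and reason.
- **Section 9.1:** add a sensitivity analysis of the Group-only failure model in all randomised participants, counting non-starters as failures. It leans against XRNTX if some of those removed would have succeeded, so it should be read beside the main result.

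The cost is wording in five places and one extra model. No new test or visit is needed, because urine and timeline follow-back are already scheduled for both arms. Some candidates who would have entered on self-report alone will enter later. A smaller XRNTX-only filter from the challenge remains, but it is reported. If the challenge falls after the baseline scan, a participant who fails it has used a scan slot. Challenging everyone before randomisation would close the remaining gap, but would impose a test that XRBUP does not need.

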4.4 End of Study Definition

A participant is considered to have completed the study if he or she has completed all phases of the study including the last visit or the last scheduled procedure shown in the Schedule of Activities (SoA), [Appendix Section 12.1](#). Proper referral and continuation of treatment after study discontinuation, with an option to continue the same medication for Vivitrol group and options to switch to oral preparation of buprenorphine or a biosimilar injectable extended release preparation that is available on the US market.. Participants will be offered referrals commensurate with their treatment preferences and the medication they received in the study. Individuals who drop out of study pharmacotherapy will be offered to continue their follow up visits. Individuals who drop out of study pharmacotherapy will be offered to continue their follow up visits. Participants completing the study will be referred to the clinical program of their choice using a “warm-handoff” procedure that will include (1) beginning to make arrangements for post-study referral before the effects of XRNTX or XRBUP wear off allowing one month for the project coordinator and the participant to establish clinical treatment (2) monitoring and assisting participants in making their follow up appointment and escorting them to their first appointment as needed (3) Providing psycho-education about opioid overdose risk and provide prescriptions for the nasal Naloxone spray used as a rescue in case of an overdose.

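### The naloxone prescription, overdose education and warm handoff are written only for study completers, although the protocol names XRNTX drop-outs as being at greater overdose risk

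*Combined protocol and SAP*

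**What the plan says.** Section 2.3.1 raises the risk twice. In the discussion of overdose it says "Individuals formerly treated with XRNTX do lose their tolerance to opioids and are therefore at an increased risk of opioid overdose", and ties this to stopping treatment abruptly, usually against medical advice. In the list of the most important XRNTX side effects it gives "loss of opioid tolerance and therefore greater risk of opioid overdose after study completion or in case of drop out".

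The remedy in section 2.3.1 begins: "to minimize the risk of overdose, participants completing the study will be referred to the clinical program of their choice". It uses a warm handoff with three parts: (1) "beginning to make arrangements for post-study referral before the effects of XRNTX or XRBUP wear off"; (2) help in making and attending the first appointment; (3) "Providing psycho-education about opioid overdose risk and provide prescriptions for the nasal Naloxone spray used as a rescue in case of an overdose".

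Section 4.4 repeats the same three parts and the same recipients: "Participants completing the study will be referred to the clinical program of their choice". It defines completion as follows: "A participant is considered to have completed the study if he or she has completed all phases of the study including the last visit". That sentence also allows the last scheduled procedure in the Schedule of Activities as the end point. Section 4.4 further says "Participants will be offered referrals commensurate with their treatment preferences and the medication they received in the study", and lets people who stop the study medication keep coming to follow-up visits.

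**The concern.** The people named as at risk and the people named to receive the remedy are not the same. The risk statement covers both those who finish and those who drop out, with particular weight on abrupt stopping. The specific protective items are a rescue prescription, overdose education and an accompanied transfer to another programme. In both places where they appear, they are assigned to those who finish.

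A coordinator following the text literally would write the naloxone prescription for someone who attends to the end. Nothing would prompt one for someone who disappears after the first or second injection. XRNTX removes opioid tolerance and its blockade lasts about a month, so the period after leaving is the one the protocol itself identifies as hazardous. This is a participant-safety matter, not a threat to the primary analysis.

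**Working it through.** The plan gives no figure to reproduce here, so the check compares the text on risk with the text on remedy and then gives an illustrative scale.

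**1. Who is at risk.** Section 2.3.1 names former XRNTX patients who stop abruptly and, in the side-effect list, both completers and drop-outs.

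**2. What follows the side-effect list.** Section 2.3.1 says the listed XRNTX risks will be minimised by certain measures. Those measures are confirmation of opioid-free status (including a naloxone challenge), treatment of anxiety, injection technique and liver-test exclusions. The word psychoeducation appears once, on the injection-technique line, with no stated content. None of these measures deals with overdose after drop-out.

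**3. Where the remedy appears.** Naloxone prescription, overdose education and warm handoff appear together in sections 2.3.1 and 4.4, both times for those who complete.

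**4. What people who leave do receive.**

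| Provision | Section | Naloxone prescription? | Dedicated overdose education? |
|---|---|---|---|
| Referral and continuation of treatment after discontinuation | 4.4 | Not stated | Not stated |
| Continued follow-up visits | 3.4, 4.4 | Not stated | Not stated |
| Remote and in-person monitoring, phone contact, retention efforts | 3.4, 4.2, 2.3.2 | Not stated | Not stated |
| Reasons for withdrawal | 7.2 | Not stated | Not stated |
| Calls and letter after missed visits | 7.3 | Not stated | Not stated |
| Consent session on side effects, safeguards and emergency procedures, with a quiz and 24-hour contact | 10.1.1.2 | Not stated | General disclosure only |

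**5. Who is left.** Someone who stops injections but attends to the last visit, or has the last scheduled procedure, may meet the section 4.4 definition and receive the full package. The group not covered is therefore mainly those who leave the study before its end.

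**6. Illustrative scale.** The inputs are the 25% dropout assumption in section 9.1 and the group sizes of 80 (section 9.2) and 70 (section 9.1).

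- 0.25 × 80 = 20 XRNTX participants
- 0.25 × 70 = 17.5, or about 18

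The 25% is stated for missing data in the secondary polysubstance analyses and is not specific to the XRNTX arm, so these counts show order of magnitude only.

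**The case against.** The strongest reply is that drop-outs are looked after. Section 4.4 offers referral after discontinuation. Sections 2.3.2, 3.4 and 4.2 describe active contact. Section 7.3 requires attempts to reach anyone who misses a required visit. Every participant is told at consent about side effects and emergency procedures and receives a 24-hour contact. All of this stands, and a reader who inferred that drop-outs are abandoned would be wrong. But none of these provisions supplies naloxone, and most of them depend on the person staying reachable.

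A second reply is that section 2.3.1 reports lower overdose rates after XRNTX discontinuation than in control groups. That rules out claiming an expected excess of overdoses from these documents. It does not remove the gap, because the protocol goes on to require mitigation anyway and only its recipients are in question.

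Third, the consent form and the DSMP are not in the supplied text and may mention naloxone. This cannot be checked, so the point is confined to what the protocol sections say.

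Three stronger readings are tempting but unsupported:

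- A reader might infer that the handoff comes too late for drop-outs because section 7.2 allows withdrawal only once an injection is more than 14 days overdue. Nothing ties the handoff or any outreach to section 7.2 withdrawal, and contact attempts start earlier.
- A reader might take the 50% retention at the third XRNTX injection in section 4.1 as an upper bound of 40 of 80. That figure is medication retention in earlier studies. It counts people who stop injections but keep attending, and misses people lost after the third injection, so it bounds nothing.
- A reader might link this to the difference between the 20-week participant duration and a schedule ending on Day 100. That is a separate matter and does not bear on who receives naloxone.

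**Conclusion.** The point holds in a limited form. As written, sections 2.3.1 and 4.4 give the naloxone prescription, overdose education and warm handoff only to completers, while section 2.3.1 names XRNTX drop-outs as at greater overdose risk. In the supplied text, people who leave early have no naloxone prescription and no dedicated overdose education.

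The size is about 20 of 80 XRNTX participants (18 of 70), as an illustration. It assumes that the 25% applies to that arm and that those who drop out do not otherwise meet the completion definition; the number is smaller if some stay to the last visit.

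The documents give no overdose rate. They support no estimate of overdoses, and no claim about the safety comparison or the stopping rule. Confidence is medium because the consent form and the DSMP were not available and staff may already give naloxone more widely. The point should be fixed because the hazard is one the protocol itself names and the remedy is cheap.

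**What to change.** Amend sections 2.3.1 and 4.4, with cross-references in 7.2 and 7.3, as follows:

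- Give the nasal naloxone prescription and the overdose education to every XRNTX recipient at or before the first injection visit, and record that this was done.
- Offer the warm handoff to anyone who discontinues, as soon as staff learn of a refusal, a missed injection or a withdrawal.

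The first item matters most because it does not depend on reaching someone who has left. The handoff cannot do that job alone. The schedule puts injections 30 days apart (Days 10, 40 and 70), and the drug effect is given as about 28 to 30 days. A handoff prompted by a missed injection would therefore start about 30 − 30 = 0 to 30 − 28 = 2 days after the effect ends.

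The cost is a protocol amendment, modest coordinator time and some extra prescriptions: on the illustration above, about 20 XRNTX participants beyond the completers already provided for. No additional patients are needed and the analysis does not change. If staff already give naloxone to everyone, the amendment only brings the text into line with practice.
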